5.2 Analysis Populations

Intention-to-Treat Population (ITT):

The primary analysis will be based on the ITT population. All randomized subjects will be analyzed according to their original randomization assignment (WATCHMAN+TAVR or TAVR) regardless of treatment received. The ITT analysis will be censored at 2 years (730 days) after randomization.

Per-protocol population (PP):

The per-protocol population is defined as patients in the WATCHMAN groups who received both the WATCHMAN and the prosthetic valve. In the TAVR only group, it is defined as patients who had the prosthetic valve placed. The PP analysis will be censored at 2 years (730 days) after randomization.

5.3 Covariates

Treatment will be the only covariate in the Cox proportional-hazards regression model.

5.4 Data Handling

5.4.1 Missing Data

Missing data will not be imputed for analysis purposes.

5.4.2 Durations

- Time to Event (e.g. time to primary endpoint) will be calculated as (event date/time – randomization date/time). Patients not having an event, or lost to follow-up will be censored at the minimum of the time of their last documented follow-up date, death date, or 2 years (730 days).
- Other durations of time will be calculated similarly as (date/time of interest – reference date/time +1)

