3 STUDY DESIGN AND ENDPOINTS

3.1 DESCRIPTION OF THE STUDY DESIGN

The WATCH-TAVR study is a prospective, multicenter, randomized trial to be conducted at approximately 33 centers in the U.S. The trial aims to enroll approximately 350 patients to accumulate the necessary 191 primary events. Enrollment is expected to occur over the course of 18 months. Patients will be followed up for a total of 2 years.

Eligible patients from each investigator's patient population shall be screened as potential candidates for the WATCH-TAVR study. The patient's history and baseline clinical parameters will be reviewed and written informed consent to participate will be obtained. The fulfillment of all inclusion and exclusion criteria shall be assessed and further baseline parameters necessary prior to randomization shall be obtained. Patients will be randomized to TAVR procedure alone or TAVR procedure combined with the WATCHMAN procedure. Determination for participation in the study is based upon standard of care practice for assessment of TAVR & WATCHMAN eligibility.

It is recommended that the procedure (TAVR or combined WATCHMAN + TAVR) should be performed within two weeks of randomization. All patients who receive the WATCHMAN device will follow the WATCHMAN Device Implant Pharmacologic Regimen (see section 6.2.4). Patients randomized to the TAVR procedure only will be treated in accordance with standard of care with either warfarin, other anticoagulant/anti-platelet therapy, or no anticoagulation at the discretion of the treating physician. All patients will continue to receive routine post-TAVR follow-up and care. Use of the WATCHMAN device in the TAVR only arm should be avoided during the first year, unless medically necessary. All enrolled study patients shall be followed up at 45 days, 6 months, 12 months and 24 months. Follow-up beyond 1 year may be in the form of an office visit or a phone call.

Patients shall be evaluated for neurological function by NIH Stroke Scale and for modified Rankin Scale (MRS) stroke disability at baseline and each visit. In addition all patients who experience a Stroke or TIA will be evaluated by a neurologist and have brain imaging.

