7.2 ADVERSE EVENT REPORTING

An adverse event is an untoward event that affects the patient's health or safety. When reporting an adverse event, the investigator will complete the AE report form.

Adverse experiences that require reporting include any adverse event with clinical symptoms that could possibly be contributed to any of the following:

- The WATCHMAN device
- The TAVR device
- The WATCHMAN implant procedure (including pericardial effusion, device embolism, stroke)
- The TAVR implant procedure (including pericardial effusion, device embolism, stroke)
- Any study required procedures (i.e., clinical complications from protocol required TEE, etc.)

The following adverse events will also be reported regardless of relationship to the device(s) or procedure(s):

- Any event with an outcome of death
- Stroke (ischemic and/or hemorrhagic) and TIA
- Any events associated with bleeding
- Arterial or venous thrombosis or embolism
- Rehospitalization related to procedure or device implantation
- Any potential Unanticipated Adverse Device Effects (see definition below)

Each adverse event will be evaluated by the investigator for relatedness and seriousness.

i) Relatedness

The relatedness of an adverse event to the study, WATCHMAN Device, TAVR device, WATCHMAN procedures or TAVR procedure will be assessed by the Investigator for each submitted adverse event form.

- **Device Related:** An adverse event that results from the presence or performance of the device or any other component of the system.

- **Procedure Related:** An adverse event that occurs due to the system implantation procedure. Adverse events that are contributable to the anesthesia or contrast media given during the implant procedure will be considered procedure related.
- **Unknown:** An adverse event that cannot be determined to have a causal relationship with either the system or procedure will be classified as unknown.
- **Not Related:** An adverse event that is determined to not have a causal relationship with either the system or procedure.

ii) Seriousness

Adverse events as described above will be evaluated for serious injury. Adverse events resulting in death or serious injury are to be reported to the sponsor within 24 hours of learning of the event. Serious injury is an injury or illness that:

- Is life-threatening, or
- Results in permanent impairment of a body function or permanent damage to a body structure, or

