9 STATISTICAL CONSIDERATIONS

9.1 STATISTICAL AND ANALYTICAL PLANS

All statistical analysis will be “intent-to-treat”, with each patient being considered as part of their randomized group irrespective of the actual treatment received. Patients not having an event, or lost to follow-up will be censored at the time of their last documented follow-up visit or phone call.

The study is designed to demonstrate the non-inferiority of the WATCHMAN device compared to the control group, with regards to the primary endpoint (composite of all-cause mortality, stroke (ischemic and hemorrhagic), or bleeding (major and/or life-threatening)). Non-inferiority will be assessed using the 1-sided 97.5% confidence interval around the hazard ratio (WATCHMAN-TAVR: TAVR only). Non-inferiority will be demonstrated if the 1-sided 97.5% upper confidence limit for the difference in proportions is less than 1.5. If the non-inferiority objective is met, additional analyses to assess superiority of the WATCHMAN group to the control group will be performed. The composite primary endpoint will also be summarized as events per 100 patient-years of follow-up.

For data collected at baseline, during the procedure and at follow-up, descriptive statistics will be generated. Continuous variables will be summarized with reporting of mean, standard deviation (SD), median, interquartile range (Q1, Q3) and range (minimum and maximum). General linear models will be used to compare continuous variables across treatment groups. Categorical variables will be summarized using counts and percentage of subjects and compared using the standard Chi-square statistic or Fisher’s Exact test, as appropriate.

In general, missing data will not be imputed and will remain missing, unless otherwise indicated.

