9.4 DESCRIPTION OF STATISTICAL METHODS

9.4.1 GENERAL APPROACH

The ITT population will be used to analyze the primary and secondary endpoints. The non-inferiority hypothesis will only be tested using the primary endpoint of all-cause mortality, stroke, and major/life-threatening bleeding. Event rates, hazard ratio and 95% confidence intervals and a p-value associated with the non-inferiority hypothesis will be provided. If the non-inferiority objective is met, a p-value for the superiority hypothesis will also be provided. Secondary endpoints will be summarized using event rates, hazard ratios and 95% confidence intervals. Nominal p-values for comparisons between treatment groups will be provided for descriptive purposes only.

All patients should be followed until the termination of the study, regardless of adherence to the treatment strategy. Available information on patients lost to follow-up will be included in the analyses. Patients not reaching a primary endpoint by the time of study termination will be censored at their last known assessment.

Statistical methods will be further outlined in the Statistical Analysis Plan (SAP).

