9.4.4 SAMPLE SIZE

The WATCH-TAVR is a randomized, prospective multi-center event-driven non-inferiority study to determine the safety and efficacy of the WATCHMAN device in patients with non-valvular AF undergoing TAVR for aortic stenosis. The control group consists of patients undergoing TAVR who are on standard medical practice, with oral anticoagulation at the discretion of the treating physician. The treatment group will have the WATCHMAN implantation procedure performed simultaneously with TAVR. The primary endpoint is a composite of all-cause mortality, stroke, life-threatening or major bleeding. The objective of the study is to demonstrate non-inferiority of the TAVR plus WATCHMAN device compared to the TAVR only group.

Data from the PARTNER¹ trial, along with the SOURCE-XT¹⁰ and FRANCE-2¹¹ registries show all-cause mortality rates in TAVR patients with AF vary from 19-30%, stroke rates from 6-10% and major/life-threatening bleeding from 17-22%. The PROTECT-AF trial for the WATCHMAN device in non-valvular atrial fibrillation patients reported a risk reduction of nearly 40% for the primary composite endpoint of stroke, systemic embolization or cardiovascular or unexplained death (RR 0.61, 95%CrI 0.42-1.07)⁴.

The following assumptions were used to determine the sample size needed to assess the non-inferiority hypothesis for the composite primary endpoint of all-cause mortality, stroke or major or life-threatening bleeding:

- One-sided $\alpha = 0.025$
- Primary event rate in the control population (TAVR only) of 35% at one year
- Non-inferiority margin of 1.5
- Underlying hazard ratio of active to control is 1.0
- Power at least 80%
- Lost to follow-up rate 10%

Assuming level of significance (α) to be 0.05 (or $\alpha = 0.025$ one-sided) and aiming for a study power ($1 - \beta$) of 80%, we estimate 191 primary events will be needed to rule out an upper limit of the one-sided 97.5% confidence interval of 1.5. Assuming an enrollment duration of 18 months, follow-up period of 24 months, and 10% drop out rate per annum, the minimum total sample size required is 350 (175 per group).

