7.2 Secondary Analyses

The Secondary endpoints will include the following:

- Time from randomization to each component of the primary endpoint:
 - All-cause mortality
 - Any stroke (ischemic and hemorrhagic)
 - Any occurrence of major or life-threatening bleeding (as per VARC2 definition of bleeding)
- Time to death from cardiovascular causes
- Time to ischemic stroke
- Time to hemorrhagic stroke
- Arterial or venous thrombosis or embolism
- Rehospitalization related to WATCHMAN procedure or WATCHMAN device.

Analysis of time-to-event endpoints for the components will be analyzed similarly to that of the primary endpoint, except there will be no testing of the non-inferiority hypothesis. Point estimates and 95% confidence intervals will be derived from a Cox proportional model with treatment group as a factor. Descriptive frequencies of the endpoints and Kaplan-Meier curves will be presented. P-values may be

provided for descriptive purposes, but should not be considered informative. The frequency of procedure related complications, device/implant failure or systemic embolism will be summarized with descriptive statistics.

KCCQ-12 score quality of life (QoL) subdomains at baseline and follow-up visits will be summarized with descriptive statistics. Change from baseline in KCCQ-12 will be analyzed using the mixed model for repeated measures (MMRM). The model will include treatment group, baseline value, visit, visit and treatment interaction. Subject will be treated as the random effect, and variance covariance component will be compound symmetry.

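### The SAP's minimum rule for censoring can cut off patients who die event-free at their last contact before death, which modestly overstates Kaplan-Meier and person-time rates for stroke, bleeding and cardiovascular death

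*SAP*

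**What the plan says.** SAP 5.4.2 (Durations) measures time to event from randomization. For anyone lost to follow-up or still event-free, the rule is that they "will be censored at the minimum of the time of their last documented follow-up date, death date, or 2 years (730 days", whichever comes first. The SAP does not define what counts as documented follow-up.

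The protocol words the rule in two other ways, and neither mentions the date of death. Section 9.1 has such patients "censored at the time of their last documented follow-up visit or phone call". Section 9.4.1 says that patients without a primary endpoint "will be censored at their last known assessment".

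SAP 7.2 carries the approach over to the secondary endpoints: "Analysis of time-to-event endpoints for the components will be analyzed similarly to that of the primary endpoint", apart from the non-inferiority test. It specifies Cox models, and "Descriptive frequencies of the endpoints and Kaplan-Meier curves will be presented". Neither document names a competing-risk method.

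On the visit schedule, Protocol 3.1 says: "All enrolled study patients shall be followed up at 45 days, 6 months, 12 months and 24 months".

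On event capture, Protocol 7.2 requires deaths, strokes and bleeding events to be reported whatever their relation to device or procedure, and "Adverse events resulting in death or serious injury are to be reported to the sponsor within 24 hours of learning of the event". SAP 7.1 counts positively adjudicated primary-endpoint events up to day 730, not only those up to the last visit.

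**The concern.** In the composite and in all-cause mortality, death is an event, so the death-date term has nothing to do there. It matters for endpoints that a patient can die without reaching: any stroke, ischemic stroke, hemorrhagic stroke, bleeding and cardiovascular death (where a non-cardiovascular death is censored). The same holds for thromboembolism and device-related rehospitalization if they are analysed as times to event.

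For these endpoints the natural censoring time for a patient followed until death is the death date. A visit or call normally precedes death, so a minimum returns the visit, and the death date operates only if a follow-up record is dated on or after death. A bleed between the last visit and death is counted, but a patient who lives through the same interval without a bleed and then dies contributes no time for it. Events and time at risk are cut at different points, and the estimated rate rises. Between the 12- and 24-month visits the discarded interval can approach a year.

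Stroke and bleeding are what readers will use to interpret the composite. The overstatement grows with mortality, so it differs between arms if mortality does.

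**Working it through.** **The plan's own figure.** The documents give no number for the censoring rule. The event target reproduces: 4 × (1.960 + 0.842)² / (ln 1.5)² = 191.0, against 191 stated. It concerns the composite and does not depend on this rule.

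**Inputs.**
- Contacts at 0, 45 days, 6, 12 and 24 months (Protocol 3.1), timed here from randomization.
- Death 19–30%, stroke 6–10%, major or life-threatening bleeding 17–22% (Protocol 9.4.4). No time horizon is given there; reading them as one-year risks is an assumption.
- Lower mortality of 10–15%, with event risks of 4% and 15%, as an assumed sensitivity range.
- Constant, independent hazards; no dropout; all events between last contact and death are reported.

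**Hand check: 19% mortality, 10% stroke.**
- Hazards per year: death −ln 0.81 = 0.2107; stroke −ln 0.90 = 0.1054; total 0.3161.
- Time at risk over two years, censoring at death: (1 − e^(−2 × 0.3161)) / 0.3161 = 1.482 years per patient.
- Stroke-free deaths: 0.2107 × 1.482 = 0.312 per patient.
- Mean time from last scheduled visit to death: 114 days = 0.312 years (simulated; integrating over the visit intervals gives the same).
- Time dropped: 0.312 × 0.312 = 0.097 years.
- Rate ratio, rule as written against censoring at death: 1.482 / (1.482 − 0.097) = 1.07.

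The same steps at 30% mortality: 1.305 years at risk, 0.466 stroke-free deaths, 107 days (0.293 years), so 0.137 years dropped, and 1.305 / (1.305 − 0.137) = 1.12.

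**Simulation, 400,000 patients per setting, two-year results, last-visit censoring against censoring at death.**

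| One-year mortality | Kaplan-Meier inflation | Rate inflation |
|---|---|---|
| 10–15% | 3–6% | 3–6% |
| 19% | 6–7% | 7% |
| 30% | 10–13% | 11–12% |

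At 19–30% mortality, about 102–116 days are dropped per event-free death, and 8–10% of those patients are censored at day 0. In points, Kaplan-Meier rises by 0.8–2.3 for stroke and 1.9–3.8 for bleeding. With half of the first-year event risk placed in the first 30 days, Kaplan-Meier inflation is 5–10%.

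**Hazard ratio, 15% one-year event risk, true value 1.**

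| Mortality by arm | Censored at death | Last visit |
|---|---|---|
| 20% v 20% | 1.003 | 1.002 |
| 30% v 30% | 0.995 | 0.994 |
| 20% v 15% | 1.004 | 0.984 |
| 30% v 20% | 0.987 | 0.946 |
| 30% v 19% | 1.004 | 0.959 |

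With equal mortality nothing moves. In the last two rows the shift is 4–5%, in favour of the arm with fewer deaths.

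**What censoring at death leaves behind (10% stroke, two years).**

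| Mortality | Kaplan-Meier, last visit | Kaplan-Meier, at death | Cumulative incidence |
|---|---|---|---|
| 19% | 20.4% | 19.1% | 15.7% |
| 30% | 21.3% | 19.1% | 13.8% |

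At 19% mortality, correcting the censoring date removes 20.4 − 19.1 = 1.3 of the 20.4 − 15.7 = 4.7 points. The remaining 3.4 points arise because Kaplan-Meier treats death as censoring.

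**The case against.** **The wording can be read harmlessly.** If a death report or the vital-status check in Protocol 4.4 is a documented follow-up date, the minimum returns the death date and the problem disappears. That reading gives the death-date term a function, and the documents do not exclude it. Against it, the protocol speaks of a visit or phone call (9.1) and of an assessment (9.4.1). Two programmers could code the rule differently and obtain different stroke and bleeding curves, which is reason enough to settle it.

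**The sizes lean high.** This stands. Protocol 6.2.3 allows for interim visits and 9.1 counts phone calls; each extra contact shortens the gap. The 30% mortality setting also fits poorly with the planned 35% one-year composite: under independent hazards, 30% death, 17% bleeding and 6% stroke give 1 − 0.70 × 0.83 × 0.94 = 45%, whereas 19% death gives 1 − 0.81 × 0.83 × 0.94 = 37%. Mortality of 30% against 19% means a mortality hazard ratio of ln 0.70 / ln 0.81 = 1.69, while the plan assumes 1.0 for the composite.

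**Censoring at death is not always right.** This stands too. If a patient was lost or withdrew and the death came to light only through a vital-status check, event status after last contact is unknown, and censoring at that contact is correct. Where strokes and bleeds before death are under-reported, censoring at death adds unverified event-free time and pulls rates down.

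**Nothing formal depends on it.** Secondary p-values are descriptive (Protocol 9.4.1, SAP 7.2). That limits the severity but does not make the estimates right.

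**Conclusion.** The point holds, as a minor one. On the more natural reading of SAP 5.4.2, a patient followed until death without a stroke or bleed is censored at the last contact before death, while events in that interval count. Kaplan-Meier estimates and person-time rates for stroke and bleeding are then too high by roughly 3–7% in relative terms at 10–19% one-year mortality, and by about 11% at 30%. These figures rest on contacts only at scheduled visits, constant hazards, full reporting of events before death, and the protocol's ranges read as one-year risks. Cardiovascular death is affected in the same direction; its size depends on non-cardiovascular mortality, which the documents do not give.

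A reader might infer three stronger things that the documents do not support:

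- **That the primary result is compromised.** It is not. Death is an event in the composite, so the composite, all-cause death, the non-inferiority test and the 191-event target are untouched. So are simple event counts.
- **That the comparison of arms is biased in general.** The hazard ratio moves only when mortality differs between arms: about 2% at 20% against 15%, and 4–5% at 30% against 19–20%.
- **That censoring at death makes the Kaplan-Meier curve correct.** The larger overstatement comes from death as a competing event, and it remains.

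**What to change.** Replace the rule in SAP 5.4.2, for every secondary time-to-event endpoint in which death is not itself the event, with:

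*Event-free patients under follow-up until death are censored at the death date; patients lost or withdrawn earlier are censored at the last date their event status is known; neither later than day 730.*

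For cardiovascular death, apply it to patients who die of other causes. Define which records establish that event status is known, and align Protocol 9.1 and 9.4.1 with the SAP.

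Keep the Cox models as cause-specific analyses. Add Aalen-Johansen cumulative incidence for stroke and bleeding with death as the competing event, and for cardiovascular death with non-cardiovascular death as the competing event.

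The cost is a few sentences in the SAP, a matching edit to the protocol and a little extra analysis. No new data are needed. The one downside is some reliance on complete event reporting between last contact and death, which Protocol 7.2 already requires.

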5.4.3 Change from Baseline

Change from baseline to post-baseline visits will be calculated as the absolute change: post-baseline value – baseline value.

[figure not shown]
5.5 Interim Analyses

No interim statistical analysis will be performed.

6 SUMMARY OF STUDY DATA

6.1 Subject Disposition

A consort flow diagram will be provided as listed below. The summary statistics will be produced in accordance with section 5.

6.2 Demographic and Baseline Variables

Descriptive statistics will be generated for all baseline patient characteristics. Continuous variables will be summarized with reporting of mean, standard deviation (SD), median, interquartile range (Q1, Q3) and range (minimum and maximum). General linear models will be used to compare continuous variables across treatment groups. Categorical variables will be summarized using counts and percentage of subjects and compared using the standard Chi-square statistic or Fisher's exact test, as appropriate.

6.3 Concurrent Illnesses and Medical Conditions

The summary statistics will be produced in accordance with section 5.

7 ANALYSES

7.1 Primary Analysis

The ITT analysis will include all positively adjudicated post-randomization primary endpoints within the ITT analysis set through 24 months (730 days) after randomization.

The study is designed to demonstrate the non-inferiority of the WATCHMAN device compared to the control group, with regards to the primary endpoint (composite of all-cause mortality, stroke (ischemic and hemorrhagic), or bleeding (major and/or life-threatening)). Non-inferiority will be assessed using the 1-sided 97.5% confidence interval around the hazard ratio (WATCHMAN-TAVR: TAVR only). Non-inferiority will be demonstrated if the 1-sided 97.5% upper confidence limit for the difference in proportions is less than 1.5. If the non-inferiority objective is met, additional analyses to assess superiority of the WATCHMAN group to the control group will be performed. The composite primary endpoint will also be summarized as events per 100 patient-years of follow-up.

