9.2 STATISTICAL HYPOTHESES

The study is designed to demonstrate the non-inferiority of the WATCHMAN device compared to the control group, with regards to the primary endpoint (composite of all-cause mortality, stroke (ischemic and hemorrhagic), bleeding (major and/or life-threatening)).

The following null hypotheses will be tested:

- H_{01} : The hazard ratio for WATCHMAN + TAVR relative to TAVR is ≥ 1.5 (non-inferiority)
- H_{02} : The hazard ratio for WATCHMAN + TAVR relative to TAVR is ≥ 1.0 (superiority)

If H_{01} is rejected, then H_{02} will also be tested. If the null hypothesis for non-inferiority is not rejected, H_{02} will not be tested.

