9.4.2 ANALYSIS OF THE PRIMARY ENDPOINT

The primary endpoint is the first occurrence of all-cause mortality, stroke or major/life-threatening bleeding event within one year following randomization. Estimates of the hazard ratio and 95% confidence intervals will be based on the Cox proportional hazards model, under the assumption of proportional hazards. Comparison of cumulative hazard functions will be based on the log-rank test.

The upper bound of the confidence interval will be generated from the Cox proportional hazards model with treatment group as a factor.

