4 SAMPLE SIZE

This randomized control trial will aim to prospectively enroll 350 patients having non-valvular AF undergoing standard care of TAVR. The control group consists of patients undergoing TAVR who are on standard medical practice, with oral anticoagulation at the discretion of the treating physician. The treatment group will have the WATCHMAN implantation procedure performed simultaneously with TAVR. The primary endpoint is a composite of all-cause mortality, stroke, life-threatening or major bleeding. The objective of the study is to demonstrate non-inferiority of the TAVR plus WATCHMAN device compared to the TAVR only group.

The following assumptions were used to determine the sample size needed to assess the non-inferiority hypothesis for the composite primary endpoint of all-cause mortality, stroke or major or life-threatening bleeding:

- One-sided $\alpha = 0.025$
- Primary event rate in the control population (TAVR only) of 35% at one year
- Non-inferiority margin of 1.5
- Underlying hazard ratio of active to control is 1.0
- Power at least 80%
- Lost to follow-up rate 10%

Assuming level of significance (α) to be 0.05 (or $\alpha = 0.025$ one-sided) and aiming for a study power ($1 - \beta$) of 80%, we estimate 191 primary events will be needed to rule out an upper limit of the one-sided 97.5%

confidence interval of 1.5. Assuming an enrollment duration of 18 months, follow-up period of 24 months, and 10% drop out rate per annum, the minimum total sample size required is 350 (175 per group).

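### The non-inferiority success rule puts the 1.5 margin on a difference in proportions, although the rest of the plan uses it as a hazard ratio

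*SAP*

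**What the plan says.** SAP 7.1 and Protocol 9.1 describe the primary comparison in two consecutive sentences. The first names the hazard ratio: "Non-inferiority will be assessed using the 1-sided 97.5% confidence interval around the hazard ratio". The second gives the decision rule and names a different statistic: "Non-inferiority will be demonstrated if the 1-sided 97.5% upper confidence limit for the difference in proportions is less than 1.5". The wording is the same in both documents. In both, superiority is then assessed only if the non-inferiority objective is met.

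Elsewhere the scale is the hazard ratio:

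- Protocol 9.2 states H01 as "The hazard ratio for WATCHMAN + TAVR relative to TAVR is" at least 1.5, and H02 as the same ratio at least 1.0.
- Protocol 9.4.2 says: "The upper bound of the confidence interval will be generated from the Cox proportional hazards model with treatment group as a factor".
- SAP 5.3 specifies a Cox model in which treatment is the only covariate.
- Protocol 9.4.4 and SAP 4 assume a true hazard ratio of 1.0, one-sided alpha of 0.025 and 80% power. The protocol concludes that "we estimate 191 primary events will be needed to rule out an upper limit of the one-sided 97.5% confidence interval of 1.5", and the SAP gives the same event count.

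The margin bullet in both sample-size sections reads only "Non-inferiority margin of 1.5", with no scale attached.

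**The concern.** Two adjacent sentences name different statistics for one decision, and the one that states the threshold names the wrong one. A value of 1.5 makes sense for a ratio. For a difference in proportions it lies outside the possible range of -1 to 1.

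The sentence is the trial's success criterion and, in SAP 7.1, the condition for going on to superiority. Applied literally, it would declare non-inferiority whatever the data showed, so that condition would screen out nothing. The SAP has no hypotheses section and no second pass/fail statement, so the correct scale has to be inferred from neighbouring text. A pre-specified success rule should not need interpreting once results are available. Because the same wording is in the protocol, neither document holds a clean version of the sentence.

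**Working it through.** **Inputs.** Margin 1.5, true hazard ratio 1.0, one-sided alpha 0.025, power 80%, control event rate 35% at one year and 191 events (SAP 4, Protocol 9.4.4). Allocation 1:1 with 175 per arm (Protocol 6.1.1). Normal quantiles are 1.960 and 0.8416, and ln 1.5 = 0.4055.

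**1. Reproduce the planned event count with 1.5 as a hazard ratio** (Schoenfeld, 1:1 allocation).

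D = 4 × (1.960 + 0.8416)² / (ln 1.5)² = 190.97, rounded up to **191**. This is the plan's figure.

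**2. What the intended rule does at 191 events.**

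- SE(log HR) = 2/√191 = 0.1447.
- Power at a true hazard ratio of 1.0: Φ(0.4055/0.1447 − 1.960) = 0.800.
- Observed hazard ratio at which the upper limit equals 1.5: 1.5 / exp(1.960 × 0.1447) = 1.130.
- Example: an observed hazard ratio of 1.2 has an upper limit of 1.2 × exp(1.960 × 0.1447) = 1.59, so the trial fails.

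**3. What the literal rule does.** The one-sided 97.5% Wald upper limit for p₁ − p₀ is

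(p₁ − p₀) + 1.960 × √[p₁(1 − p₁)/175 + p₀(1 − p₀)/175].

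Over every combination of 0 to 175 events in each arm, the maximum is **1.005**. It occurs, for example, at 174/175 with the device and 0/175 without: 0.9943 + 1.960 × √(0.9943 × 0.0057/175) = 0.9943 + 0.0112 = 1.0055. The limit never reaches 1.5. Even the most unfavourable outcome possible would count as non-inferior.

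The sample size confirms that this scale was not the design scale. A non-inferiority calculation on proportions with 35% in both arms and a margin of 1.5 gives (1.960 + 0.8416)² × 2 × 0.35 × 0.65 / 1.5² = 1.6, that is, 2 patients per arm.

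**4. What a hazard ratio of 1.5 means as a difference.** The plan does not state a hazard shape, so I assume a constant control hazard that gives 35% at one year, with proportional hazards.

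| Time | Control | Device at HR 1.5 | Difference |
|---|---|---|---|
| 1 year | 1 − 0.65 = 35.0% | 1 − 0.65^1.5 = 47.6% | 0.126 |
| 2 years | 1 − 0.65² = 57.7% | 1 − 0.65³ = 72.5% | 0.148 |

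The number in the sentence is therefore 10 to 12 times the difference that the design margin implies (1.5/0.148 = 10.1; 1.5/0.126 = 11.9).

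**The case against.** The best counter-argument is that nobody would be misled. The preceding sentence names the hazard ratio, a limit of 1.5 is visibly impossible for a difference, and an analyst could hardly run the literal rule without noticing. A wrong but plausible margin, such as 0.15, would be more dangerous. Neither document gives a difference-in-proportions method for the primary endpoint. In SAP 4, the bullet after the margin gives the assumed effect as a hazard ratio, and SAP 5.3 names the Cox model. Protocol 9.2 also makes the test of H02 conditional on rejecting H01, which is stated on the hazard-ratio scale.

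Most of this stands. The intent is clear, and the loss of the superiority gate follows only if the sentence is read alone; Protocol 9.2 keeps a proper gate. Stating the scale in the margin bullets is a tidy-up rather than a necessity. These points show what the sentence should say, but they do not make it say so. The SAP still has no other explicit success rule, and a reader must set aside its literal text to apply the right one.

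Two limits on the argument should be noted. The 1.13 threshold applies at 191 events; SAP 5.1 also allows a final analysis after an administrative stop, when it would differ. Protocol 9.4.2 is cited here only for the source of the upper bound. Its one-year endpoint window differs from the 730 days in SAP 7.1, which is a separate matter that this correction does not settle.

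**Conclusion.** The concern holds. The success criterion for the primary endpoint is wrong as written in both documents: it names a statistic that cannot reach the stated threshold, and it contradicts the adjacent sentence, H01, the Cox analysis and the 191-event calculation. It is most plausibly a drafting slip, with one evident intended reading.

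The practical effect on the design is nil, because sample size, alpha and power were derived on the hazard-ratio scale. The gap between the two readings is total: one rule can never fail, while the other requires an observed hazard ratio below about 1.13 at 191 events. I rate it as a must-fix because of where the error sits, not because a wrong analysis is likely. The event count and the impossibility of reaching 1.5 need no assumption beyond the plan's own inputs. The 0.126 and 0.148 equivalents rest on a constant control hazard and proportional hazards.

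**What to change.** In SAP 7.1 and Protocol 9.1, replace the decision sentence with wording such as:

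> Non-inferiority is concluded if the upper limit of the one-sided 97.5% confidence interval for the hazard ratio (TAVR plus WATCHMAN versus TAVR alone), estimated from the Cox model with treatment as the only covariate, is below 1.5.

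In SAP 4 and Protocol 9.4.4, add to the margin bullet that 1.5 is a hazard ratio, so that the SAP states the scale itself.

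The cost is one sentence and one bullet in each document, with no new data or patients and no change to sample size, alpha or power. Make the change, with a dated record, before any comparative results are seen, so that no question arises of the scale having been chosen afterwards.
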